of low dose GC in terms of bone health has been emerging, where prednisolone ≤ 5 mg daily did not seem to be associated with reduced bone-mineral density in the recent Glucocorticoid-induced Osteoporosis in Patients With Chronic Inflammatory Rheumatic Diseases or Psoriasis (Rh-GIOP) study (27). The GLORIA trial also provide partial reassurance with regard to infection risk which is another most recognized adverse event of GC therapy. After 2 years of 5mg/day prednisolone, the proportion of patients (all aged ≥ 65) with at least one adverse event of special interest (serious or glucocorticoids-related) was increased by 24%, mostly due to non-severe infections. The result sets a benchmark for the upper limit of harm, and the risk in a less vulnerable population with lower dose and shorter duration of GC use is expected to be lower. All in all, “*does the concomitant use of GCs at very low doses increase therapeutic success without producing unacceptable side effects?*” is explicitly listed as one of the top research agenda in the latest EULAR RA management recommendations published in 2023 (6).

We believe the half-a-century long controversy regarding GC use in RA boils down to one final clinical question that whether very low dose GC is an effective and safe bridging therapy, as 1) chronic GC use is unanimously not advisable, 2) very low dose GC (prednisolone < 5 mg/day) appears to have no or minimal toxicity concern (28), and 3) prednisolone 4mg daily shows promising therapeutic effect in our preliminary study. Very low dose GC could be the universal add-on treatment for all RA patients initiating csDMARDs with an optimal benefit-risk ratio. To formally address this important clinical question, we plan to perform the first randomized controlled trial assessing the efficacy and safety of prednisolone 4 mg/day added to standard of care in patients with newly diagnosed RA. The results of our study are anticipated to be immediately implemental and can guide daily clinical practice.

c. Aims and Hypotheses to be Tested:

The aim of this study is to evaluate the efficacy of prednisolone 4mg/day added to standard of care in newly diagnosed RA patients with active disease. We hypothesise add-on prednisolone 4mg/day is efficacious compared to placebo in newly diagnosed RA patients with active disease.

d. Plan of Investigation:

(i) Study design

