This is an investigator-initiated, single-center, randomized, placebo-controlled, double-blind study. The intervention duration is 10 weeks. The follow-up period is 24 weeks. The recruitment period is 30 months. The total study duration will be 3 years.

(ii) Methods

Primary outcome

The primary outcome is the change of DAS28-CRP at 4 weeks comparing prednisolone group and placebo group.

Secondary outcomes

- 1) Changes of RA disease activity at week-8, week-12 and week 24 comparing the 2 groups.
- 2) Changes of RA disease activity at different time points within the 2 groups.
- 3) Disability at different time points comparing the 2 groups.
- 4) Proportion of patients with adverse events comparing the 2 groups.
- 5) Independent predictors of RA disease control in all participants.

Treatment and clinical evaluations

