All the participants (n=112) will be randomized in a 1:1 ratio to prednisolone (n=56) or placebo (n=56) group. Randomization will be performed using a computer-generated randomization list provided by the research pharmacist, adopting a permuted blocks design with block sizes of 4. Allocation concealment will be ensured by the use of sequentially numbered, opaque, sealed envelopes. Treatment will be masked to patients and investigators. The participants will be instructed to take one study capsule (prednisolone or placebo) daily for 10 weeks. For the prednisolone group, the dose of the active drug will be 4mg once daily for 4 weeks then tapering at 1mg/week every 2-week till off at week 10. All participants will also be given csDMARDs and treated to a target of DAS28 low disease activity (<3.2) at Prince of Wales Hospital (PWH) throughout the study period according to a standard protocol modified to our study based on the EULAR recommendation and the Hong Kong guideline on the use of DMARDs. Disease activity and adverse events will be monitored at 4 weeks, 8 weeks, 12 weeks and 24 weeks. Patients will be advised to reach out to the rheumatologists earlier if the condition changes unexpectedly. Changes in the dosage or addition of nonsteroidal anti-inflammatory drugs are allowed. Switching to a new csDMARD is possible in case of toxicity or intolerance. The use of b/tsDMARDs or additional systemic GC will be prohibited throughout the study. All medication changes will be documented in detail. Participants who required rescue b/tsDMARDs or systemic GC will be withdrawn from the study. They will be treated according to the standard of care with regular assessment till the end of the study. All patients will be given calcium and vitamin D supplements throughout the study period.

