A sample size determination was conducted for the primary outcome measurement, the difference in the change of DAS28-CRP at 4 weeks comparing the 2 groups, using Power Analysis and Sample Size Software (PASS version 11). From the published results of the GLORIA trial, the short-term (3 months) improvement in DAS28 in the prednisolone group and placebo group was 1.36 ± 1.14 (baseline 4.40 ± 1.04) and 0.73 ± 1.21 (baseline 4.46 ± 0.99) respectively (21). In our pilot study mentioned above, the improvement in mean DAS28 was -1.4 ± 1.3 post-treatment. Therefore, more conservatively, we expect the difference of the change of DAS28-CRP at 4 weeks to be 0.6 comparing the prednisolone and placebo group. At least 49 patients will be required in each group to achieve a statistical power of 0.8 with a two-sided α of 0.05. With an estimated dropout rate of 15%, a total sample size of 112 would be required.

The study will be submitted to The Joint Chinese University of Hong Kong – New Territories East Cluster Clinical Research Ethics Committee and the Central Institutional Research Board of the Hospital Authority for approval. It will also be submitted to the clinicaltrials.gov for registration. Written informed consent will be obtained from all participants prior to any of the trial procedure. The study will be conducted according to the Declaration of Helsinki and ICH-GCP guidelines.

(iv) Data processing and analysis

Patients who discontinue treatment or violate treatment protocol will be excluded from the analysis (per-protocol analysis). Missing data are assumed missing at random and will be treated using a multiple imputation method. Descriptive statistics will be used to present the baseline demographic and clinical variables included frequencies, means with standard

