deviations and median with interquartile range. T-test or Mann-Whitney U test and Chi-square test or fisher exact test will be used to evaluate the differences in clinical variables between the prednisolone and the placebo group at baseline, depending on the data distribution. The primary outcome measurement, the difference in the change of DAS28-CRP at 4 weeks comparing the 2 groups, will be analyzed by T-test. Clinical variables which are significantly different between the 2 groups in the univariate analyses and are biologically plausible (eg. age, sex, disease duration, disease activity or treatment) will be adjusted in the multivariate logistic regression model to confirm the prednisolone treatment effect. The secondary outcomes on disease activity at week 8, week 12 and week 24 or disability in terms of HAQ at different time points will be compared likewise. The within group changes of these measurements before and after treatment will be examined using paired t-test or Wilcoxon signed-rank test. To look for the changes across study period across 2 groups, the repeated ANOVA test will be performed. To address the secondary outcome of comparison of proportion of patients with AE in the 2 groups, Chi-square test will be performed and cross-checked by generalized estimating equation (GEE) analysis. Sensitivity analysis using an intention-to-treat approach including all randomized patients will be done. A 2-tailed probability value of $p<0.05$ is considered statistically significant. Calculation will be performed using IBM SPSS Statistics Version 24 (IBM, Armonk, NY, USA).

(v) Potential pitfalls and contingency plans

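### The primary analysis of this superiority trial is per-protocol and intention-to-treat is only a sensitivity analysis, so response-related exclusions can bias the main result in either direction

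*Protocol*

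**What the plan says.** Protocol section d(iv), Data processing and analysis, sets the main analysis population: "Patients who discontinue treatment or violate treatment protocol will be excluded from the analysis (per-protocol analysis". Later in the same section the alternative is given a supporting role: "Sensitivity analysis using an intention-to-treat approach including all randomized patients will be done". The primary test is fixed there too: "the difference in the change of DAS28-CRP at 4 weeks comparing the 2 groups, will be analyzed by T-test".

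The objective in section c is efficacy against placebo: "We hypothesise add-on prednisolone 4mg/day is efficacious compared to placebo in newly diagnosed RA patients with active disease". No non-inferiority or equivalence margin appears anywhere. The endpoint in section d(ii) is early: "The primary outcome is the change of DAS28-CRP at 4 weeks comparing prednisolone group and placebo group". Section d(i) gives a longer treatment period: "The intervention duration is 10 weeks".

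Under Treatment and clinical evaluations in d(ii), additional systemic glucocorticoid and b/tsDMARDs are prohibited, and "Participants who required rescue b/tsDMARDs or systemic GC will be withdrawn from the study". The next sentence reads: "They will be treated according to the standard of care with regular assessment till the end of the study".

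No section gives a reason for choosing per-protocol, or says which analysis prevails if the two disagree.

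**The concern.** Stopping treatment, breaking the protocol and needing rescue all happen after randomisation and can depend on both response and arm. If prednisolone works, lack of effect and rescue should be commoner on placebo, so the worst placebo outcomes leave the comparison and a real effect is hidden. Intolerance or failure on prednisolone works the other way and can create or inflate an effect. The toxicity section foresees this second route by listing adverse events that lead to drug discontinuation as events of special interest.

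Two features make it worse. The exclusion rule is not limited to events before week 4, so something that happens between weeks 4 and 10 can remove a primary measurement already taken. And the week 8, 12 and 24 comparisons are to be made in the same way, at times when rescue has had longer to accumulate.

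Multiple imputation, planned in the same section, does not obviously help. Read literally, the exclusion comes first, and imputation then fills gaps only among the patients who remain. What is at stake is the primary conclusion: once exclusion is related to outcome and differs by arm, neither the estimated difference nor the 5% error rate is protected by randomisation.

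**Working it through.** **Inputs from the protocol.** 56 per arm (d(ii)). Expected difference 0.6, change SDs 1.14 (prednisolone) and 1.21 (placebo) from the cited controlled trial, two-sided α 0.05, power 0.80, at least 49 per group, 15% dropout (d(iii)). **Assumed:** the exclusion rates and how strongly exclusion depends on poor response. The protocol gives neither; 15% is its dropout figure, borrowed here.

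**1. The plan's own power figure.** n = 2(1.96 + 0.842)² SD²/0.6². The protocol does not state the SD used. n = 49 corresponds to SD ≈ 1.06; the pooled quoted SD, √[(1.14² + 1.21²)/2] = 1.176, gives 61. That gap is a separate matter, so power is shown for both SDs (t-test, difference 0.6):

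| Set | SD 1.176 | SD 1.06 |
|---|---|---|
| All randomised, 56 per arm | 0.76 | 0.84 |
| After 15% exclusion, 56 × 0.85 = 47.6 per arm | 0.69 | 0.78 |

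This is the loss from smaller numbers alone, before any bias.

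**2. Bound on the bias.** Removing the lowest 15% of a normal distribution raises its mean by φ(z₀.₁₅)/0.85 = 0.274 SD.
- Placebo loses its poorest responders, prednisolone exclusions random: 0.274 × 1.21 = 0.33, and 0.60 − 0.33 = **0.27**.
- The reverse: 0.274 × 1.14 = 0.31, and 0.60 + 0.31 = **0.91**.

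Simulation removing exactly 8 of 56 (14.3%) gives 0.29 and 0.89. In the first case power is about 0.27, against 0.76 for all randomised.

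**3. Milder selection in one arm.** The log-odds of exclusion rise by 1 per SD of poorer response, with 15% excluded per arm. The estimate is about 0.44 (selection on placebo) or 0.75 (selection on prednisolone). At 5% excluded it is about 0.55 or 0.65.

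**4. Same mechanism in both arms, different rates.** Exclusion follows a latent score with correlation ρ to poor response; SD 1.175, true difference 0.60. Per-protocol estimates:

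| Excluded, placebo / prednisolone | ρ = 0.3 | ρ = 0.5 | ρ = 0.8 |
|---|---|---|---|
| 15% / 15% | 0.60 | 0.60 | 0.60 |
| 20% / 10% | 0.55 | 0.51 | 0.46 |
| 25% / 5% | 0.49 | 0.42 | 0.31 |
| 10% / 20% | 0.66 | 0.69 | 0.75 |
| 5% / 25% | 0.71 | 0.79 | 0.90 |

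**5. No true effect, 56 per arm.** Two-sided rejection rate under the model of step 4, and the part that favours prednisolone (nominal 2.5%):

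| Excluded, placebo / prednisolone | ρ = 0.5 | ρ = 0.8 |
|---|---|---|
| 15% / 15% | 4.9% (2.4%) | 5.0% (2.6%) |
| 25% / 5% | 12.7% (0.3%) | 27.6% (under 0.1%) |
| 5% / 25% | 12.4% (12.1%) | 26.7% (26.6%) |

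Under the one-arm model of steps 2 and 3, at about 15% excluded, the two-sided rate is about 9–11% with mild selection and 27–31% at the bound. At 5% excluded with mild selection it stays at about 5–6%.

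**The case against.** The largest figures depend on one-sided selection, and the most extreme are bounds rather than forecasts. With the same mild selection at the same rate in both arms, the estimate stays at 0.59–0.60 and the error rate at about 5%. At 5% exclusion the bias is small. The 15% is a dropout figure, not a prediction of per-protocol exclusions. The route that seems most likely, loss of placebo failures, works against prednisolone, so the extra null rejections it produces are almost never false claims of efficacy. Treatment is double-blind, and the analysis of all randomised patients is prespecified, so a conflict between the two would be visible.

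All of this stands as a limit on size and direction, but it does not justify the choice. Equal loss by the same mechanism cannot be assumed when one arm may work better or be less well tolerated, and it cannot be verified from the patients who remain. Exclusions could also exceed 15%, because the rule covers the whole treatment period. A visible conflict does not help if the protocol has already named the per-protocol result as the main one.

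Two further cautions are fair. The assessments foreseen after rescue may mean routine clinical care rather than study DAS28-CRP visits. And the order of exclusion and imputation is a reading of the text, not something it states.

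**Conclusion.** The concern holds. The protocol explicitly makes per-protocol the main analysis and all-randomised a sensitivity analysis in a superiority trial, and nothing elsewhere reverses or justifies this. Exclusion is linked to response through rescue and is not confined to the period before the week-4 endpoint.

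The size cannot be known from the document. With 15% excluded per arm, the quoted SDs and selection in one arm only, a true difference of 0.60 would appear as about 0.44 or 0.75 under mild selection, and at most 0.27 or 0.91. With no true effect, the two-sided rejection rate would be about 10% under mild selection and about 30% at the bound. It falsely favours prednisolone only when that arm loses more of its poor responders. The bias shrinks towards zero if exclusions are few, unrelated to response, or alike in the two arms. The finding is that the type I error and the estimate are no longer guaranteed, not that they must be wrong. Because this affects the primary conclusion and costs little to correct, it must be fixed.

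**What to change.** In section d(iv), make all randomised patients, analysed in the arm to which they were allocated, the primary set for week-4 DAS28-CRP and for the between-group secondary comparisons. State that values recorded after discontinuation, protocol violation or rescue are used, and that multiple imputation applies only to values that are actually missing. Move per-protocol to the sensitivity analysis, and limit its exclusions for the week-4 endpoint to events before that visit.

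In section d(ii), reconcile the sentence that withdraws rescued patients from the study with the next one, which continues their assessment. It should be clear that they leave study treatment but stay in data collection, with DAS28-CRP recorded at the planned visits.

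The cost is a wording change that swaps two analyses already planned, with no extra patients. If the continued assessments were meant only as routine care, recording DAS28-CRP at them is a small addition for the few patients concerned. The all-randomised estimate may be slightly diluted by non-adherence; the per-protocol sensitivity analysis remains available for comparison.

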To monitor the possible side effect of prednisolone and other medications, complete blood count, liver function test and renal function test will be performed at screening, week 4, week 8 and week 12 and week 24. Body mass index, blood pressure, blood sugar and lipid profile will be checked at baseline, week 4, week 8, week 12 and week 24. Chest x-rays will be obtained at screening and when clinically indicated. Hepatitis status and electrocardiogram will be done at screening. The treating physicians will record all adverse events (AEs) and, if necessary, make treatment adjustments in accordance with the protocol. Serious AEs (SAEs) are defined as the occurrence of life-threatening condition or death, a significant or permanent disability, a malignancy, hospitalization or prolongation of hospitalization, a congenital abnormality, or a birth defect. AEs of special interest (AESI) will also be collected which include any AE leading to drug discontinuation, MACE (myocardial infarction, cerebrovascular or peripheral arterial vascular event), newly occurring hypertension/diabetes/infection/cataract/glaucoma and fragility fracture.

iii) Subjects (with justification on the sample size)

Consecutive RA patients attending the rheumatology clinics of PWH will be screened for eligibility. The inclusion criteria are: 1) ≥ 18 year-old, 2) fulfilment of the 2010 ACR/EULAR classification criteria of RA, 3) never use of any DMARDs for RA, 4) disease activity score 28-C-reactive protein (DAS28-CRP) > 3.2 , and 5) Chinese subjects only. The exclusion criteria are: 1) pregnancy or premenopausal women planning pregnancy, 2) functional status class IV (limited in ability to perform usual self-care, vocational, and avocational activities), 3) use of systemic GC in recent one month, and 4) contraindications to prednisolone. A total of 112 patients who meet the criteria will be included.

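### As written, the per-protocol exclusion also governs the main adverse-event comparison, which then omits every patient who stopped the capsule because of an adverse event

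*Protocol*

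**What the plan says.** Section d(iv), Data processing and analysis, opens with the analysis set: "Patients who discontinue treatment or violate treatment protocol will be excluded from the analysis (per-protocol analysis". No outcome is named, so the rule is not confined to the primary or efficacy outcomes.

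Later in the same section comes the safety analysis: "To address the secondary outcome of comparison of proportion of patients with AE in the 2 groups, Chi-square test will be performed", cross-checked by GEE. No safety set is named. The next sentence reads: "Sensitivity analysis using an intention-to-treat approach including all randomized patients will be done". It too names no outcomes.

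Under Toxicity monitoring, "The treating physicians will record all adverse events (AEs"), and the events singled out include those that end treatment: "AEs of special interest (AESI) will also be collected which include any AE leading to drug discontinuation".

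Two statements under Treatment and clinical evaluations affect who is excluded. "Participants who required rescue b/tsDMARDs or systemic GC will be withdrawn from the study", and of these patients the protocol adds: "They will be treated according to the standard of care with regular assessment till the end of the study". By contrast, "Switching to a new csDMARD is possible in case of toxicity or intolerance", so an AE that leads only to a change of background csDMARD need not remove the patient.

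**The concern.** A patient who stops the capsule because of an AE has, by definition, had an AE. A rule that drops patients who discontinue therefore removes patients from the AE comparison because of the outcome being compared. It also conflicts with the protocol's own list of events of special interest. For capsule stops, patients with an AE that led to discontinuation are exactly the patients excluded, so in the per-protocol set that count is zero in both arms by construction.

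Patients withdrawn for rescue and other protocol violators are dropped as well, and some of them will have had no AE. Their removal pushes an arm's AE proportion the other way.

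The result at stake is the main between-arm AE comparison. The formal aim in section c is efficacy, and AEs are a secondary outcome with no power claim. Even so, the Introduction presents the trial as assessing safety as well as efficacy, and the AE comparison is where that is delivered.

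**Working it through.** **Reading the rules together**

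1. Section d(iv) excludes discontinuers and violators from the analysis, without limiting this to any outcome.
2. The AE chi-square test is specified in the same section, with no exemption.
3. So the main AE comparison uses the per-protocol set.
4. A patient who stopped the capsule for an AE is a discontinuer and is outside that set.
5. Multiple imputation, also in d(iv), does not bring such a patient back: it fills in values within the analysis set.
6. The intention-to-treat sentence, read as broadly as the exclusion, does bring the patient back, but under the label of a sensitivity analysis.

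**What the exclusion can do to the result**

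Inputs from the protocol: 56 patients per arm (Treatment and clinical evaluations) and a 15% dropout allowance (section d(iii)), which is 0.15 × 56 = 8.4, or about 8 per arm. The protocol states no AE or AE-stop rate for this trial, so all AE counts below are assumptions.

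Let A and B be the patients with an AE on prednisolone and placebo, and a and b those of them who stopped the capsule because of it, with no other exclusions.

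- All patients: A/56 − B/56
- Per-protocol: (A − a)/(56 − a) − (B − b)/(56 − b)

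| A vs B | a vs b | All patients | Per-protocol | Effect |
|---|---|---|---|---|
| 20 vs 12 | 4 vs 1 | 8/56 = 14.3 points | 16/52 − 11/55 = 30.8 − 20.0 = 10.8 | shrinks |
| 20 vs 12 | 1 vs 4 | 14.3 points | 19/55 − 8/52 = 34.5 − 15.4 = 19.2 | widens |
| 28 vs 16 | 5 vs 4 | 12/56 = 21.4 points | 23/51 − 12/52 = 45.1 − 23.1 = 22.0 | almost unchanged |
| 20 vs 16 | 8 vs 0 | 4/56 = 7.1 points | 12/48 − 16/56 = 25.0 − 28.6 = −3.6 | reverses |

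In the second row the uncorrected chi-square p-value moves from 0.094 to 0.023. The fourth row is an extreme: it spends the whole dropout allowance of one arm on AE stops and has none in the other.

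**Within one arm.** Removing AE stops alone always lowers the proportion. From 20/56 = 35.7%, 1, 4 or 8 AE stops give 19/55 = 34.5%, 16/52 = 30.8% or 12/48 = 25.0%.

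**Adding exclusions without an AE.** Take the first row and also remove rescue withdrawals who had no AE, 1 versus 6 (assumed). The difference becomes 16/51 − 11/49 = 31.4 − 22.4 = 8.9 points. The placebo proportion rises from 20.0% to 22.4% only because patients without an AE left the denominator.

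**The case against.** The strongest reply is that the exclusion was meant for efficacy. It is labelled per-protocol, all AEs are to be recorded, and a SAP, which was not seen here, could define a safety set. The intention is probably as described. But the protocol does not leave the point open for a SAP to fill. It states an exclusion rule that, as worded, reaches the AE test.

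A second reply is that the intention-to-treat sentence follows directly after the AE test and is just as general. If the exclusion covers AEs, so does the all-randomised analysis, and the complete comparison is already planned. That is fair, and it narrows the problem to which of the two results is the main one. It does not remove the problem, because the main result is then the selected one.

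Three further points limit the weight:

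- The protocol plans no formal comparison of events of special interest, and nothing prevents them from being listed for all patients. The zero count applies only to a tabulation in the per-protocol set.
- Capsules are taken for 10 of the 24 weeks, so an AE that starts after week 10 cannot cause a capsule stop. Rescue withdrawal, however, can still occur later.
- The illustrations rest on assumed counts. They show what is possible, not what is likely.

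None of these changes the fact that the main AE comparison has the wrong set as written.

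**Conclusion.** The concern holds: the rule is wrong as written for the AE comparison and should be changed. It makes the main AE comparison depend on who stopped because of an AE. Under the assumed counts, with 56 per arm, a difference of 14.3 points became anything from 8.9 to 19.2, and one of 7.1 points became −3.6 in an extreme case. The real size and direction cannot be determined, because the protocol gives no AE or AE-stop rates and the effect depends on how AE stops, other AEs and other exclusions fall by arm.

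The conclusion rests on the literal reading of d(iv); the intention was probably narrower. This point concerns the safety result only.

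**What to change.** In section d(iv), state that the per-protocol exclusion applies to efficacy analyses only. Add that the main summaries and comparisons of AEs, serious AEs and AEs of special interest include every randomised patient who took at least one study capsule, regardless of discontinuation, rescue or protocol violation.

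The cost is one or two sentences, with no new visits or procedures, since all AEs are already recorded. One limit should be acknowledged: the protocol states continued assessment to the end of the study only for patients withdrawn for rescue, so AE data after other capsule stops may be less complete. The AE that led to the stop is recorded either way.

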We have conducted a pilot open-label study evaluating the efficacy of add-on prednisolone 4mg daily in patients with recently diagnosed RA [unpublished]. We recruited 7 consecutive patients not on any DMARDs with at least moderate disease activity from 11/23 to 1/24. Their baseline clinical characteristics are shown in table 1. Prednisolone 4mg daily was started together with methotrexate. The participants were reassessed in 4 weeks. Improvement in RA disease activity was noted in most of the patients post-treatment. The mean Disease Activity Score 28–C-Reactive Protein (DAS28-CRP) decreased from 5.1 ± 0.7 to 3.7 ± 1.6 ($p=0.042$). There was no significant adverse event reported. However, as there was no control group, the results were confounder by the therapeutic effect of methotrexate. It is of note that from our large local real-world RA database, about a quarter of the exposure to GC (in terms of person-year interval) was below prednisolone 5mg daily, indirectly reflecting the clinical effectiveness and possibly safety of very low dose GC (19).

Despite the advent of biologic and targeted synthetic DMARDs, there is a trend in the RA research field to revisit the effect and safety of low dose GC (25). Back in 2016, the EULAR task force re-evaluated the harm and safety of low dose GC use, and proposed that the risk of long-term prednisolone ≤ 5 mg daily was acceptably low (26). Evidence in favor of the safety

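### Baseline DAS28-CRP enters the analysis only if the arms differ significantly, and then through a logistic model that does not fit the continuous primary outcome; a prespecified linear model with baseline as covariate is a free improvement

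*Protocol*

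**What the plan says.** The outcome is defined in section d(ii), Primary outcome: "The primary outcome is the change of DAS28-CRP at 4 weeks comparing prednisolone group and placebo group". It is a difference between two scores on a continuous scale.

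Section d(iv), Data processing and analysis, fixes three things:

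- **Primary test.** "The primary outcome measurement, the difference in the change of DAS28-CRP at 4 weeks comparing the 2 groups, will be analyzed by T-test".
- **Which variables are adjusted for.** "Clinical variables which are significantly different between the 2 groups in the univariate analyses and are biologically plausible". Disease activity is one of the examples given.
- **The adjusting model.** Those variables "will be adjusted in the multivariate logistic regression model to confirm the prednisolone treatment effect".

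Disease activity at weeks 8, 12 and 24 follows the same plan, and "disability in terms of HAQ at different time points will be compared likewise". For allocation, section d(ii) describes "adopting a permuted blocks design with block sizes of 4" and mentions no stratification factor.

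No linear model with baseline DAS28-CRP as a covariate appears anywhere. The multivariable adjustment mentioned in section d(v) concerns NSAID and csDMARD use after randomisation, which is a different matter.

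**The concern.** There are three linked weaknesses.

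1. **The model does not match the outcome.** Logistic regression needs a binary response, and the protocol ties no binary response to this analysis. To run the confirming model, someone would have to choose a cut-point or another model later, possibly with outcome data in view.

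2. **The covariate trigger is a poor rule.** Under randomisation a significant baseline difference is a chance event, expected in about 5% of trials. On the natural reading, baseline disease activity is ignored in the other 95%, however prognostic it is. The reason to adjust for a baseline score is its relation to the outcome, not the p-value of a baseline comparison.

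3. **Precision may be given up.** A t-test on change fixes the coefficient of baseline at 1. A linear model estimates it, and in large samples is at least as precise. It also removes the bias that, conditional on an observed imbalance, sits in the change-score estimate.

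**Working it through.** **Inputs**

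- Cited 5 mg trial, section d(iii): "improvement in DAS28 in the prednisolone group and placebo group was 1.36 ± 1.14 (baseline 4.40 ± 1.04) and 0.73 ± 1.21", with a placebo baseline SD of 0.99. These are 3-month data.
- Pilot, section b(ii): DAS28-CRP "decreased from 5.1 ± 0.7 to 3.7 ± 1.6". Section d(iii) gives the SD of change as 1.3.
- Planned difference 0.6, two-sided α 0.05, power 0.8, 49 evaluable per group (section d(iii)).

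**The plan's own figure.** Pooled SD of change = √((1.14² + 1.21²)/2) = 1.176. The t-test then needs 2 × (1.960 + 0.842)² × 1.176² / 0.6² = 60.3, that is 61 per group (62 by the t distribution), not 49. At 49 per group its power is 0.706. The protocol does not say which SD gave 49; an SD of about 1.04 to 1.06 would. This is a separate matter, but it is why the unadjusted reference below is 0.71 and not 0.80.

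**Gain from adjusting for baseline.** Pooled baseline SD: SD₀ = √((1.04² + 0.99²)/2) = 1.015. The follow-up SD (SD₁) is not in the protocol, so it is assumed over a range.

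- Covariance = (SD₀² + SD₁² − SD_change²)/2
- Slope = covariance / SD₀²
- Residual variance = SD₁² − covariance² / SD₀²

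Example at SD₁ = 1.0: covariance = (1.031 + 1.000 − 1.382)/2 = 0.3245; slope = 0.315; residual variance = 1.000 − 0.3245²/1.031 = 0.898. Reduction = 1 − 0.898/1.382 = 35%.

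| Assumed SD₁ | Slope | Residual SD | Variance reduction | Power, 49 per group |
|---|---|---|---|---|
| 1.0 | 0.32 | 0.948 | 35% | 0.873 |
| 1.1 | 0.42 | 1.015 | 25% | 0.825 |
| 1.2 | 0.53 | 1.073 | 17% | 0.782 |
| 1.3 | 0.65 | 1.120 | 9% | 0.747 |
| 1.4 | 0.78 | 1.154 | 4% | 0.721 |
| 1.5 | 0.92 | 1.173 | 0.5% | 0.708 |
| 1.55 | 0.995 | 1.176 | 0% | 0.706 |
| 1.6 | 1.07 | 1.173 | 0.4% | 0.707 |
| *t-test on change* | 1 (fixed) | 1.176 | – | 0.706 |

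Power uses the noncentral t with 95 degrees of freedom for the adjusted model and 96 for the t-test.

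Pilot SDs (0.7, 1.6, change 1.3): covariance = (0.49 + 2.56 − 1.69)/2 = 0.68; slope = 1.39; residual variance = 2.56 − 0.68²/0.49 = 1.616; reduction = 1 − 1.616/1.69 = 4.4%. Power moves from 0.619 to 0.638.

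**What the trigger requires.** With 49 per group and baseline SD 1.015, the arms must differ by 1.985 × 1.015 × √(2/49) = 0.41 points to reach p < 0.05. An imbalance just below that shifts the change-score estimate, conditionally, by (1 − slope) × 0.41: 0.28 at SD₁ 1.0, 0.19 at 1.2, 0.09 at 1.4 and about 0 at 1.55. With the pilot SDs the threshold is 0.28 and the shift is 0.11 in the opposite direction. Averaged over randomisations these shifts are already in the t-test's standard error; they are not an additional error.

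**Simulation.** In 40,000 trials with 49 per group and a true difference of −0.6, both estimators averaged −0.60, and the trigger fired in 5% of trials. Power for the t-test and the prespecified linear model was 0.704 and 0.868 at SD₁ 1.0, 0.707 and 0.779 at 1.2, 0.710 and 0.722 at 1.4, and 0.706 and 0.702 at 1.55.

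**The case against.** The strongest reply is that the primary analysis is not wrong. The t-test on change matches the outcome definition and the sample-size basis, and it is unbiased. This stands: on the t-test alone, the point is about precision.

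Second, the gain is unproven. It runs from 35% to nothing on an assumed SD, and the only data from this dose, visit and kind of patient give about 4%. The larger gains borrow from a trial in patients over 65, at 3 months, with entry at DAS28 ≥ 2.6 against DAS28-CRP > 3.2 here, and the protocol reports its score only as DAS28. A narrower baseline spread would lower the gain: combining the pilot's baseline SD of 0.7 with the change SD of 1.176 gives about 28%, 7% and 0.3% at SD₁ 1.0, 1.2 and 1.4. This stands too, so no single figure should be quoted. The pilot, however, has only 6 or 7 patients and cannot settle the matter the other way.

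Third, binary outcomes do exist in the protocol: the low-disease-activity target and ACR20/50/70. The secondary outcome on predictors of disease control is a natural use for logistic regression, and the word may be a slip. But none of these is tied to confirming the effect on the primary outcome, so the text still needs correcting.

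Fourth, some readings are inferences. The univariate analyses are not defined, although the baseline comparisons described just before are the natural candidate. The week 8, 12 and 24 and HAQ comparisons may inherit only the t-test. The absence of stratification is read from silence. None of this rescues the logistic model for a continuous change score.

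Nor is this detail left to an analysis plan: the protocol itself fixes the test, the covariate rule and the model type.

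**Conclusion.** The point holds and should be corrected. Two parts rest on the text alone: the confirming model does not fit the stated outcome, and the significance trigger is an unsound way to choose covariates. The third, lost precision, is real in direction but of unknown size. With the cited trial's SDs it lies between a 35% variance reduction (power 0.87 against 0.71) and nil for follow-up SDs from 1.0 to 1.55; with the pilot SDs it is about 4%. The recommendation does not depend on which case applies, since the worst case is the loss of one degree of freedom. The protocol gives no HAQ data, so no gain is claimed there. The validity of the t-test is not in dispute.

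**What to change.** In section d(iv):

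- Make the primary analysis a linear model of week-4 DAS28-CRP (or its change) on treatment, with baseline DAS28-CRP as a prespecified covariate. Report the adjusted mean difference with its 95% confidence interval.
- Use the same form for weeks 8, 12 and 24, and for HAQ with its own baseline value.
- Delete the significance-triggered logistic adjustment for these continuous outcomes. If logistic regression is meant for a binary outcome such as disease control, name that outcome.
- Keep the t-test on change as a supportive analysis.

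The cost is two rewritten sentences and one degree of freedom. Baseline DAS28-CRP is already needed for eligibility, and the planned software fits the model. The change has to be made before unblinding to count as prespecified.
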